4.2. Secondary End Points + Time Points

-To study if early intervention with Zilucoplan® is safe (number of AEs/SAEs)

-To study if early intervention with Zilucoplan® affects clinical outcome

defined by 6-point ordinal scale change between day 1 and respectively day 6, day 15 (or discharge, whichever comes first) and day 28 (by phone call). 6-point ordinal scale defined as

1. Death
2. Hospitalized, on invasive mechanical ventilation or ECMO;
3. Hospitalized, on non-invasive ventilation or high flow oxygen devices;
4. Hospitalized, requiring supplemental oxygen
5. Hospitalized, not requiring supplemental oxygen

Not hospitalized

-Number of days requiring supplemental oxygen after randomization to Day 28 (or discharge, whichever comes first)

-Number of days with fever (defined as 37.1°C or more) during 28-day assessment period

- change from baseline in SOFA score to D6, D15 (or on discharge, whichever is first)

- Time to at least a 2-point improvement or discharge sustained up to D28 on the 6-point ordinal scale during 28-day assessment period

-Incidence of nosocomial bacterial or invasive fungal infection during 28-day assessment period

Patients with viral respiratory infection are at risk of secondary bacterial infections. As part of routine clinical care, sputum or BAL samples will be collected in patients suspected of secondary bacterial

pneumonia, and checked for the presence of bacteria. Measurements of procalcitonin levels will be performed at least three times per week until day 14 or hospital discharge.

- **All-cause mortality rate at 28 days post randomization (all treated participants)**
- All-cause mortality rate at 28 days post randomization (excluding participants that required invasive mechanical ventilation or ECMO, non-invasive mechanical ventilation or high-flow oxygen devices within 24 hours prior to or after randomization)**
- All-cause mortality rate at 28 days post randomization (excluding participants that required invasive mechanical ventilation or ECMO within 24 hours prior to or after randomization)**
- All-cause mortality rate at 28 days post randomization (only including patients that required invasive mechanical ventilation or ECMO within 24 hours prior to or after randomization)**
- Incidence of patients in each category of the 6-point Ordinal Scale at follow up 12-22 weeks post-randomization**
- All cause mortality at follow up 12-22 weeks post-randomization for all treated participants**

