4.3. Exploratory Endpoints

- Time since randomization until improvement in oxygenation, (defined as independence from supplemental oxygen) during 28-day assessment period (or discharge, whichever comes earlier)**
- Number of days with hypoxia defined as SpO₂ < 93% breathing room air or the dependence on supplemental oxygen after randomization to Day 28 (or discharge, whichever comes earlier)**
- Time since randomization until absence of last fever (defined as 37.1°C or more) for more than 48h without antipyretics**
- **change in CRP levels between day 1 and day 6, and between day 1 and day 15 (or discharge in each case**
- **change in ferritin levels between day 1 and day 6, and between day 1 and day 15 (or discharge in each case).**
- Incidence of SARs/SUSARs during 28 days**
- Duration of hospital stay**
- Duration of hospital stay in survivors**
- **Change from baseline in 6-point ordinal scale to Day 6, Day 15 and D28 (by phonecall) post randomization**

- Percentage of participants reporting at least a 2-point improvement sustained to D28 or discharge
- AUEC/Time using the 6-point score recorded daily – up to D15, D28 and all data recorded
- Percentage of participants who record a 2-point improvement from baseline or discharge at D6, D15 and D28
- Percentage of participants not deteriorating according to the ordinal scale by 1 or 2 points on D6, D15 and D28
- 6-point Ordinal Scale at 6 and 15 days (or discharge whichever comes first) and day 28 (phone call), in relation to serum D-dimers and complement C5a levels at baseline

- Time since randomization until first use of high-flow oxygen devices or non-invasive mechanical ventilation or invasive mechanical ventilation or ECMO in non-ventilated patients (i.e. excluding patients who are ventilated within 24h prior to or after randomization) during 28-day assessment period
- duration of ventilator-free days after randomization to Day 28 (or discharge, whichever comes earlier)
- Duration of invasive mechanical (including ECMO) and non-invasive mechanical ventilation in ventilated patients
- Duration of ICU stay in patients that enrolled in trial on invasive or non-invasive mechanical ventilation for less than 24h prior to or after randomization during 28-day assessment period
- Duration of ICU stay in patients that enrolled in trial that were on invasive or non-invasive mechanical ventilation or high-flow oxygen devices within 24h prior to or after randomization during 28-day assessment period

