
Objective 2
 
Number of days with hypoxia (defined as SpO₂ <93% breathing room air or the dependence on supplemental oxygen after randomisation to Day 28 (or discharge, whichever comes earlier)
	
Use SpO₂ (%) and Suppl O₂ (Y/N) from Vital parameters to derive indicator variable which flags each day where this condition holds.
 
Derive variable per participant that gives total number of days with condition
	
Summary statistics of variable with Total number of days: n, mean, SD, median, minimum, maximum
 
By treatment arm

Endpoint	Derivation	Analysis

Objective 3 Duration of ventilator free days after randomisation to Day 28 (or discharge, whichever comes earlier)
	
Use data from Vital parameters (include all days, where NIV, IV and ECMO='N')
	
Summary statistics of variable with Total number of days: n, mean, SD, median, minimum, maximum By treatment arm

Objective 3 Duration of invasive mechanical (including ECMO) and non-invasive mechanical ventilation in ventilated participants
	
Complement of above (exclude participants who are not ventilated i.e. do not include these with a duration of 0)
	
Summary statistics of variable with Total number of days: n, mean, SD, median, minimum, maximum By treatment arm

Objective 3 Time since randomization until first use of high-flow oxygen devices or non-invasive mechanical ventilation or invasive mechanical ventilation or ECMO in non-ventilated participants (i.e. excluding participants who are ventilated within 24h prior to or after randomization) during 28-day assessment period
	
Use Vital Parameter CRF and the method of supplementary oxygen variable. Use the date from this CRF to identify when first use occurred. Indicator variable to identify sub-group to be included. Censor if never used any of these ventilation methods at Day 28
	
Kaplan-Meier analysis using PROC LIFETEST. Strata ACTARM. Request Survival plot adjusting axis and heading titles to reflect progression and not response Output statistics: Appropriate statistics from analysis as indicated in mock shell

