
Objective 3 Time since randomization to progression to ARDS
	
Randomisation date Date of ARDS diagnosis Derive time variable (days) from date of randomization to date of ARDs diagnosis for each participant. For participants who
	
Kaplan-Meier analysis using PROC LIFETEST. Strata ACTARM. Request Survival plot adjusting axis and heading titles to reflect progression and not response

Endpoint	Derivation	Analysis
	
do not progress to ARDs, time is from date of randomization to date of discharge from hospital or 28 days, whichever is earlier.
 
Derive Censor variable indicating whether Progression to ARDS (censor=0, otherwise censor=1)
	
Output statistics:
 
Appropriate statistics from analysis as indicated in mock shell

Objective 3
 
Duration of ICU stay in participants that enrolled in trial that were on invasive or non-invasive mechanical ventilation or high-flow oxygen devices within 24h prior to or after randomization during 28-day assessment period
 
Duration of ICU stay in participants that enrolled in trial that were on invasive or non-invasive mechanical ventilation for less than 24h prior to or after randomization during 28-day assessment period
	
Use DATES and Vital Signs dataset to calculate variable giving total number of days in ICU for sub-group of patients
	
Summary statistics of variable with Total number of days: n, mean, SD, median, minimum, maximum
 
By treatment arm

Endpoint	Derivation	Analysis

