
Objective 6 All-cause mortality rate at 28 days post randomisation (all treated participants)
 
All-cause mortality rate at 28 days post randomisation (excluding participants that required invasive mechanical ventilation or ECMO, non-invasive mechanical ventilation or high-flow oxygen devices within 24 hours prior to or after randomisation)
 
All-cause mortality rate at 28 days post randomisation (excluding participants that required invasive mechanical ventilation or ECMO within 24 hours prior to or after randomisation)
 
All-cause mortality rate at 28 days post randomisation (excluding participants that required invasive mechanical ventilation or ECMO, non-invasive mechanical ventilation or high-flow oxygen devices within 24 hours prior to or after randomisation)
 
All-cause mortality rate at 28 days post randomisation (only including participants that required invasive
	
Using 6 point ordinal scores, DATES and VITAL SIGNS and SuppO2 variables :
 
Derive indicator variable identifying each sub-group of patients identified in the Endpoint column
 
Derive Mortality variable identifying whether a patient has died within 28 days of randomisation
	
For each mortality sub-group: PROC LOGISTIC Model: Mortality=ACTARM Output percentage died on each treatment and 95% confidence interval. Odds ratio and 95% confidence interval

Endpoint	Derivation	Analysis

mechanical ventilation or ECMO within 24 hours prior to or after randomisation)
 
All-cause mortality at follow up 12-22 weeks post-randomisation for all treated participants
		

Objective 5
 
Incidents of participants in each category of the 6-point ordinal scale at follow-up 12-22 weeks post randomisation
	
6-point ordinal score
	
PROC FREQ to create summary table of actual counts and percentages for each of the 6-points on the ordinal scale at follow-up by treatment arm

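### Three 28-day mortality subgroups and the time-to-first-support population are selected partly on respiratory support in the 24 hours after randomisation (minor)

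*SAP*

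**What the plan says.** **Mortality.** Protocol 4.2, SAP 2.2.1.2 and SAP Table 8.1 (section 8.2) list 28-day mortality in all treated participants and in restricted groups. One group is defined by "excluding participants that required invasive mechanical ventilation or ECMO within 24 hours prior to or after randomisation". A second also excludes non-invasive ventilation and high-flow oxygen in the same window. The third is "only including patients that required invasive mechanical ventilation or ECMO within 24 hours prior to or after randomization". The SAP prints four restricted rows, but one is a duplicate, so three are distinct. Table 8.1 builds the subgroup indicator from the endpoint wording. It then fits a logistic regression with actual arm as the only term and reports an odds ratio with a 95% confidence interval.

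**Time to first support.** Protocol 4.3 defines this "in non-ventilated patients (i.e. excluding patients who are ventilated within 24h prior to or after randomization"); SAP Table 8.1 repeats the rule ("i.e. excluding participants who are ventilated within 24h prior to or after randomization"). The event is first high-flow oxygen, non-invasive or invasive ventilation, or ECMO, shown by Kaplan-Meier curves by arm. SAP 2.2.1.2 starts every time-to-event clock at randomisation. For dating, the SAP says "Use the date from this CRF to identify when first use occurred"; for censoring, "Censor if never used any of these ventilation methods at Day 28".

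**ICU stay.** The first ICU-stay population uses the same window ("or high-flow oxygen devices within 24h prior to or after randomization during 28-day assessment period") but is only summarised by arm. The wording of the second could mean either a duration or a window.

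No section limits membership to pre-randomisation data, gives a reason for the post-randomisation half of the window, or plans a baseline-only version. SAP 4.7 calls subgroup examination not applicable.

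**The concern.** Randomisation makes the arms comparable at randomisation. A subgroup fixed at that moment keeps this property; one that depends on the next 24 hours need not. Allocation is known, so a decision to escalate support can depend on it. If dosing is prompt, escalation can also depend on the drug, because Protocol 8.1.4 puts complete complement inhibition at about 3 hours after a dose. Patients who escalate are likely to be sicker. If they leave one arm's subgroup more often, the remaining groups differ by more than treatment.

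For time to first support the problem is internal to the definition. First-day ventilation is part of what the curve should show, yet those patients are removed after the clock has started.

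SAP 4.4.2 raises the stakes a little. Interim 2 assesses the 28-day mortality endpoints, may serve as the final analysis of key secondary endpoints, and may guide further research.

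**Working it through.** The documents give no figure for these subgroups, so there is none to reproduce. Only the 54 and 27 patients (Protocol 11.1, SAP 2.4) come from the plan. **Every other input below is assumed.**

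**1. Mortality, exclusion subgroup.** Assume that all patients start unsupported, that 25% are borderline with 25% mortality, that the rest have 4%, and that the drug has no effect on death. Let p be the share of borderline patients who escalate in the first 24 hours. Mortality among those left is

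[0.75×0.04 + 0.25×(1−p)×0.25] / [0.75 + 0.25×(1−p)]

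- p = 0.25: 0.076875/0.9375 = 8.2%
- p = 0.50: 0.06125/0.875 = 7.0%
- p = 0.20: 0.080/0.95 = 8.42%
- p = 0.60: 0.055/0.85 = 6.47%

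| p, Arm A v Arm B | Left in analysis | Expected deaths | OR (Wald 95% CI) | Shift in ln OR |
|---|---|---|---|---|
| 0.25 v 0.25 | 50.6 v 25.3 | 4.2 v 2.1 | 1.00 | 0 |
| 0.25 v 0.50 | 50.6 v 23.6 | 4.2 v 1.7 | 1.19 (0.18–7.7) | 0.171/0.955 = 0.18 SE |
| 0.20 v 0.60 | 51.3 v 23.0 | 4.3 v 1.5 | 1.33 (0.19–9.2) | 0.285/0.986 = 0.29 SE |
| 0.50 v 0.25 | 47.3 v 25.3 | 3.3 v 2.1 | 0.84 (0.14–5.1) | −0.171/0.922 = −0.19 SE |

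In rows 2 and 3 the spurious excess, on the scale of the remaining controls, is 23.6×(0.082−0.070) = 0.28 and 23.0×(0.0842−0.0647) = 0.45 of a death. If the borderline share runs from 10% to 40% and borderline mortality from 15% to 40%, the odds ratio in those two scenarios is 1.06 to 1.51. At the top corner the shift is 0.413/0.789 = 0.52 SE.

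**2. Mortality, inclusion-only subgroup.** Assume 10% are supported at baseline (45% mortality) and 10% of controls start in the window (30% mortality). Controls: (0.045+0.030)/0.20 = 37.5%. If Arm A has half the starts: (0.045+0.015)/0.15 = 40.0%. The odds ratio is (0.40/0.60)/(0.375/0.625) = 1.11 with no effect on death. With 5% to 15% starters it is 1.09 to 1.12 if starts are halved, and 0.94 if they are raised by half.

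**3. Time to first support.** Keep the 25% borderline share and treat escalation as ventilation. Assume later first-use risk of 50% in borderline patients and 10% in others, with p = 0.25 v 0.50.

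- As specified, [0.75×0.10 + 0.25×(1−p)×0.50]/(1−0.25p): 0.16875/0.9375 = 18.0% v 0.1375/0.875 = 15.7%. Difference +2.3 points (SE 9.2).
- Counted from randomisation, 0.25p + 0.75×0.10 + 0.25×(1−p)×0.50: 23.1% v 26.25%. Difference −3.1 points (SE 10.2).
- Events removed: 0.0625/0.23125 = 27% in Arm A and 0.125/0.2625 = 48% in Arm B.

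The sign changes here because fewer first-day starts were assumed in Arm A. With equal p both differences are zero, though 27% of events are still lost in each arm at p = 0.25. A more extreme choice (later risks 60% and 5%, p = 0.20 v 0.60) gives +5.1 points as specified and −4.0 from randomisation, with SEs of 8.4 and 10.0.

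**The case against.** The strongest reply is about weight. SAP 3.1 gives no p-values for secondary endpoints, SAP 4.5 calls those hypotheses exploratory, and Protocol 4.3 lists time to first support as exploratory. All-treated 28-day mortality does not use the window. SAP 8.2 replaces models by listings, figures and summaries when events are few, which is likely with about two to four expected deaths per arm. SAP 4.1 already allows baseline ordinal severity as a covariate. Ventilator-free days ("include all days, where NIV, IV and ECMO" set to no) keep first-day ventilation. All of this stands and limits the consequence. It does not remove the flaw: summaries by arm in the same groups carry the same selection, and the SAP 4.1 covariate is optional.

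The illustrations are also fair game. They assume that everyone starts unsupported, whereas eligibility admits patients on high-flow oxygen or ventilation. The unsupported groups could be smaller and the standard errors larger. A two- to threefold difference in first-day escalation has no basis in the documents.

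A reader might infer that the subgroup odds ratios are biased in a known direction, or that the window falls on treatment. The documents support neither. No escalation rates are given. On timing, SAP 2 assumes dosing very soon after randomisation, while SAP 2.2.1.2 expects about 24 hours. If the latter holds, the window is largely pre-dose. The two statements must be reconciled; the window is post-randomisation under either.

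**Conclusion.** The definitions are wrong as written, and the point is minor. Three mortality odds ratios and one pair of Kaplan-Meier curves compare groups formed partly after randomisation, and the curves omit first-day ventilation after their clock has started. This follows from the text and needs no assumption.

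Size and direction are unknown. With equal first-day escalation the mortality odds ratio is undistorted. In the main assumed scenarios the shift is under 0.3 of a standard error and under half a death; wider assumed ranges reach about half a standard error. The time-to-support differences, including the change of sign, lie well inside their standard errors. It would go too far to conclude that the trial's mortality result is compromised, because the all-treated analysis does not depend on the window.

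**What to change.** In Protocol 4.2 and 4.3, SAP 2.2.1.2 and SAP Table 8.1:

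1. Delete *or after* from the three mortality subgroups, the time-to-first-support population and the first ICU-stay population.
2. Use one rule in both arms: classify by the respiratory-support category in effect at randomisation, taken from the last pre-randomisation record. That is the screening ventilation method (SAP 2.2.4.3), or the ordinal category of SAP 4.1 where it was scored before randomisation. Protocol 9.2 ties that score to first drug administration, so this needs checking. Do not add a separate 24-hour look-back: it is a different rule, and a screening record is not a 24-hour history.
3. In time to first support, include everyone not on high-flow oxygen, non-invasive or invasive ventilation, or ECMO at randomisation. Count first use after randomisation, including on day one, as an event, and name the endpoint accordingly.
4. Where a randomisation-day record cannot be ordered against randomisation, resolve it from source times without reference to arm. Show results with such starts treated as baseline support and as events.
5. Define *ventilated*. The censoring rule groups high-flow oxygen with the ventilation methods; the ventilator-free-days rule does not. State whether the second ICU-stay wording is a duration or a window.
6. Keep the current window only as a labelled sensitivity analysis.

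The cost is wording, some reprogramming and a check of record times, with no extra patients or visits. There are downsides. Subgroup sizes change by an amount the documents do not give. First use is dated only to the day. First-day starts counted as events can still reflect open-label decisions. The analysis also remains on the dosed, as-treated set (SAP 3.5). The change should be made and dated before database lock, and labelled as made after any interim look already taken.

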2.1.2 Secondary objective(s)

The secondary objectives are:

- to study if early intervention with Zilucoplan® is safe
- to study if early intervention with Zilucoplan® affects clinical outcome defined by duration of hospital stay, 6-point ordinal scale, time to defervescence, supplemental oxygen use SOFA score,
- to study if early intervention with Zilucoplan® affects progression to mechanical ventilation and/or ARDS and duration of ICU stay
- to study if early intervention with Zilucoplan® affects the rate of nosocomial infection
- to study if treatment with Zilucoplan® has a favourable effect on long term at follow up 12-22 weeks post-randomisation
- to study if treatment with Zilucoplan® affects all-cause mortality rate at day 28 and at 12-22 weeks post-randomisation

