2.2.4.2 Safety endpoint(s) of special interest

Endpoints associated with nosocomial infection:

- Number of participants with at least one occurrence of nosocomial bacterial or invasive fungal infection for 28 days (phone call) after enrolment in trial

Participants with viral respiratory infection are at risk of secondary bacterial infections. As part of routine clinical care, sputum or BAL samples will be collected in participants suspected of secondary bacterial pneumonia, and checked for the presence of bacteria. Measurements of procalcitonin levels will be performed at least three times per week until day 14 or hospital discharge

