
Objective 5
 
Incidents of lung fibrosis on chest high-resolution computed tomography (HRCT) scan at follow up 12-22 weeks post-randomisation
 
Incidents of lung function abnormalities at follow up 12-22 weeks post-randomisation
	
HRCT results
 
Lung function results – dataset should list all abnormalities in a consistent way across participants, including ‘None’
	
Summarise Left lower, Left middle and Left Upper Total Scores by treatment
 
Summarise Right lower, Right middle and Right Upper Total Scores by treatment
 
Provide 100% stacked bars for each of the above 6 areas, coding by score (normal, reticular, bronch and honeycomb) – a separate graph for each treatment

Objective 5
 
Results from the 6-minute walk test
		

Endpoint	Derivation	Analysis

Objective 5
 
Incidents of participants in each category of the WHO performance scale
	
WHO score
	
Summary statistics of WHO Score by treatment at follow-up

Objective 4
 
Incidence of nosocomial bacterial or invasive fungal infection during 28-day assessment period
 
Note: Participants with viral respiratory infection are at risk of secondary bacterial infections. As part of clinical routine care, sputum or BAL samples will be collected in participants suspected of secondary bacterial pneumonia and checked for presence of bacteria. Measurements of procalcitonin levels will be performed at least 3x/week until 14 days or hospital discharge
	
Procalcitonine will be concentrations. Concentrations are to be taken 3 times a week. The actual day each week may differ between participants. Allocate 1, 2 or 3 to each concentration taken in chronological order in each week.
 
Replace ‘Not Detectable’ with the lower limit of quantification and include in the summary statistics.
 
Data for bacteria will be presence/absence at each day tested (if collected)
	
Summarise procalcitonine concentrations by occasion (1,2,3) within each period of 7 relative days post first-dose for each treatment.
 
Summary statistics to include n, nmissing, Mean, SD, Median, Minimum, Maximum. n in each case will be N-Not Done(nmissing).
 
Provide line plots over relative day by treatment. A separate line for each participant
 
Depending on distribution of data the above summary statistics will be provided using the log scale, and presented after back transforming

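### SAP Table 8.1 plans only procalcitonin summaries for the 28-day nosocomial infection endpoint: no infection variable is derived and no between-arm estimate is specified

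*SAP*

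**What the plan says.** The objective in SAP 2.1.2, also in Protocol 3.2, is "to study if early intervention with Zilucoplan® affects the rate of nosocomial infection". Protocol 4.2 gives the endpoint as "Incidence of nosocomial bacterial or invasive fungal infection during 28-day assessment period". SAP 2.2.1.2 lists the same endpoint. SAP 2.2.4.2 repeats it as the safety endpoint of special interest, in a form that can be counted directly: "Number of participants with at least one occurrence of nosocomial bacterial or invasive fungal infection for 28 days (phone call) after enrolment in trial".

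Table 8.1 in SAP 8.2 is where each secondary endpoint is given its derivation and analysis. In the nosocomial infection row (labelled Objective 4), the analysis column opens with "Summarise procalcitonine concentrations by occasion (1,2,3) within each period of 7 relative days post first-dose for each treatment". It continues with the descriptive statistics to be shown, line plots per participant, and a possible log scale. The derivation column numbers the procalcitonin samples within each week and says how undetectable values are replaced. Its one line on infection data is "Data for bacteria will be presence/absence at each day tested (if collected", and no output uses those data. SAP 2.2.4.2 gives the sampling schedule: "Measurements of procalcitonin levels will be performed at least three times per week until day 14 or hospital discharge".

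**The concern.** The row is headed by one variable and analyses another. An infection is an event that a participant does or does not have by day 28. Procalcitonin is a laboratory concentration, and its planned sampling covers about half of that window at most. A programmer who follows the row produces a biomarker table and plots. Nothing in the row counts infected participants, and nothing compares the arms.

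At stake is a named secondary objective that is also the SAP's safety endpoint of special interest. Without a pre-specified event definition and estimate, an infection result would have to be defined after the data are seen, in an open-label trial. Alternatively, the absence of a visible difference in procalcitonin could be read as reassurance about infection, which it cannot give.

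**Working it through.** **1. Endpoint against analysis**

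| Feature | Endpoint (Protocol 4.2, SAP 2.2.1.2, SAP 2.2.4.2) | Analysis (SAP Table 8.1) |
|---|---|---|
| Variable | At least one infection, yes/no | Procalcitonin concentration |
| Organisms | Bacterial and invasive fungal | Bacteria presence/absence, if collected; no fungal item |
| Window | 28 days | To day 14 or discharge |
| Output | Incidence by arm | Summary statistics and line plots |
| Between-arm estimate | Needed for the objective | None |

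**2. Comparable endpoints in the same table.** Protocol 11.2 assigns logistic regression to response rates and gives 28-day mortality as its example. Table 8.1 applies that method to mortality ("Output percentage died on each treatment and 95% confidence interval. Odds ratio and 95% confidence interval") and to the sustained 2-point response. Infection by day 28 is also binary over 28 days, but receives no such analysis. SAP 3.1 promises 95% confidence limits for secondary comparisons as described in section 8, and this row describes no comparison.

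**3. Rest of the SAP.** Section 10 does not take up the endpoint defined in 2.2.4.2. Section 10.2 tabulates treatment-emergent events by preferred term and treatment. Section 3.1 promises descriptive statistics by treatment for all endpoints. Neither defines when an infection counts as nosocomial, and neither gives a difference between arms.

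**4. Precision of the missing estimate.** The documents state no figure for this endpoint; their power statement concerns PaO₂/FiO₂ only. Inputs are 54 and 27 participants (SAP 2.4), all analysed, and an infection rate p that is equal in both arms. The values of p are assumptions.

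Half-width of the 95% CI for the risk difference (Wald) = 1.96 × √[p(1 − p)(1/54 + 1/27)].

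Since 1/54 + 1/27 = 0.0556, and 1.96 × √0.0556 = 0.462, this is 0.462 × √[p(1 − p)]:

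- p = 10%: 0.462 × 0.300 = 0.139
- p = 15%: 0.462 × 0.357 = 0.165
- p = 20%: 0.462 × 0.400 = 0.185
- p = 30%: 0.462 × 0.458 = 0.212

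For an odds ratio of 1, the SE of the log odds ratio is √(1/a + 1/b + 1/c + 1/d), where a to d are the expected numbers with and without infection in each arm:

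- p = 10% (5.4, 48.6, 2.7, 24.3): SE = 0.786; 95% CI = exp(±1.96 × 0.786) = 0.21 to 4.66
- p = 30% (16.2, 37.8, 8.1, 18.9): SE = 0.514; 95% CI = exp(±1.96 × 0.514) = 0.36 to 2.74

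**The case against.** The strongest reply is that the SAP is not silent on infection outside this row. A reader might infer from Table 8.1 that the trial will report no infection data at all. The documents do not support that. SAP 3.1 commits to number and percentage for categorical parameters and to descriptive tables by treatment for all endpoints, and Protocol 11.2 says all secondary endpoints will be summarized. Infections reported as adverse events would appear by arm in the SAP 10.2 tables, from first dose to the D28 visit. SAP 8.2 also refers to table shells for further detail, and these are not among the documents. The 6-minute walk test row has an empty analysis cell, so Table 8.1 is not a complete list of outputs. Many other secondary endpoints are descriptive only, and SAP 4.5 calls the secondary hypotheses exploratory.

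This limits the point without removing it. Counts may appear, but by preferred term, so a participant with two types of infection falls on two rows. Several signs that can accompany infection, such as fever and falls in blood pressure or oxygen saturation, are excluded from adverse event reporting (Protocol 13.5, SAP 10.2). That makes those tables a weaker source. A shell should not have to supply the event definition and estimator for a named objective.

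Three further inferences also go too far:

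- **That nosocomial infection is the known hazard of C5 inhibition.** Protocol 2.2 and 8.1.8 tie the risk to encapsulated bacteria, above all *Neisseria meningitidis*, and not to hospital-acquired bacterial or fungal infection in general.
- **That the interval would show how much harm from the drug is excluded.** Under Protocol 8.2, prophylactic antibiotics continue until at least 14 days after the last Zilucoplan dose in Arm A and for at most one week in Arm B. The contrast is drug plus longer prophylaxis against control.
- **That the data are already in hand.** SAP 2.2.4.2 names an endpoint, which does not prove that an eCRF field exists, and Table 8.1 makes the bacterial data conditional on collection.

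**Conclusion.** The concern holds for the endpoint-specific analysis. The Table 8.1 row specifies a different variable from its endpoint, over a shorter window, and neither it nor section 10 derives the infection variable or specifies a between-arm estimate with an interval. It should be corrected. It does not affect the primary analysis.

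The estimate would be imprecise, with a risk-difference half-width of about 14 to 21 percentage points. This assumes 54 v 27 analysed, equal rates of 10% to 30% in both arms (not given in the documents), and a Wald interval, which is approximate at 2.7 expected control-arm events. Low precision is a reason to show the interval, so that an apparent absence of difference is not taken as evidence of safety. A competing-risk analysis with death as the competing event would be a reasonable extra, but nothing in the documents requires it.

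**What to change.** In the Objective 4 row of Table 8.1, with a cross-reference from SAP section 10:

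1. Derive a yes/no variable for at least one nosocomial infection, bacterial or invasive fungal, up to day 28. State what makes an infection nosocomial and how death, discharge or withdrawal before day 28 is handled.
2. Name the data source (adverse event records and culture results, including fungal) and confirm against the eCRF that it was collected.
3. Report n (%) per arm with an odds ratio, or a risk difference, and 95% CI, by the logistic method already used for mortality. SAP 8.2 lets models be dropped when events are few, so state that n (%) with exact intervals, already used elsewhere in Table 8.1, will still be given.
4. Keep the procalcitonin summaries as supportive. Reconcile the row's rule for undetectable values (the limit of quantification) with SAP 4.2.1 (half that limit).
5. State that planned prophylaxis is longer in Arm A, so the contrast is not of the drug alone.

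The cost is a small amount of derivation work and one added table. It rises if the eCRF check shows that infection data must be retrieved from source records.
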